4.2. TREATMENT PHASE

4.2.1. Randomization (V2)

Visit 2 (Day 0) defined as day of first Ampligen[®] or placebo administration.

Subjects who meet the eligibility criteria will have completed the following evaluations and assessments at V2:

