2.6.3 Exploratory Outcome Measures

• Changes from baseline in COVID-19-related symptoms using Symptom Burden Questionnaire for Long COVID (SBQ-LC) during the course of the treatment phase.

Note: A set of common COVID-19-related symptoms (see Symptom Burden Questionnaire for Long COVID (SBQ-LC)) will be evaluated at each scheduled study visit by the patient regardless of which symptoms a subject had at baseline, as new symptoms may appear following the baseline assessment.

- Change from baseline in cognitive function as measured by Montreal Cognitive Assessment (MoCA) at week 4, 8, and 13 during the treatment phase.
- Incidence of hospitalization during the treatment phase.
- Duration (days) of hospitalization during the treatment phase.
- Evaluation of lymphocyte profile by flow cytometry in patients with post-COVID-19 conditions.

• Identification and evaluation of plasma protein biomarkers in patients with post-COVID-19 conditions.

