7.8.3 Duration (days) of hospitalization during the treatment phase

The duration (days) of hospitalization during the treatment phase will be calculated using the formula noted below.

Duration (days) = (Date of discharge - Date of hospitalization) + 1Duration (days) of hospitalization during the treatment phase will only be calculated for hospitalization(s) occurring after the date of first study treatment administration and prior to the date of last study treatment administration. For subject who remain hospitalized at the time of last treatment administration, the date of last treatment will be used for the calculation.

All deaths within 91 days will be considered censored on Day 91. Conceptually, a death corresponds to an infinite length of hospitalization but censoring at any time greater than or equal to Day 91 gives the same answer as censoring at Day 91; both correspond to giving deaths the worst rank.

In the incidence where there are multiple hospitalizations for a subject, the durations from the multiple hospitalizations will be summed to provide total duration of hospitalization for the subject.

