8.2.3.3 Incidence of hospitalization during the treatment phase

The proportion of subjects with at least one hospitalization during the treatment phase will be presented for the two treatment groups.

Similar

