8.3.1 Adverse Events

Adverse events will be classified by system organ class (SOC) and preferred term (PT) according to the most recent version of MedDRA dictionary.

TEAE are defined as adverse events with onset date on or after the first treatment. TEAEs will be summarized by treatment group, System Organ Class, and preferred term. The following TEAE summaries will be provided:

- a) Overall (*i.e.*, regardless of severity or relationship to treatment)
- b) Adverse events by severity
- c) Related adverse events by severity
- d) Adverse events leading to treatment discontinuation by severity

e) Adverse events leading to death by severity

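### SAP 7.8.3 opens the hospital-day window strictly after the first-dose date, so on its plain wording an admission on Day 0 after the first infusion gets no duration

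*SAP*

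**What the plan says.** SAP 2.6.3 lists "Duration (days) of hospitalization during the treatment phase" as an exploratory outcome. SAP 7.8.3 defines it as discharge date minus admission date plus one, summed over stays. It then limits which stays qualify: the duration is worked out only for "hospitalization(s) occurring after the date of first study treatment administration" and, at the other end, "prior to the date of last study treatment administration". Both limits are calendar dates, and both are strict.

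Protocol 4.2.1, which sits under the Treatment Phase heading, says that Visit 2 (Day 0) is "defined as day of first Ampligen[®] or placebo administration".

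Two neighbouring rules are relevant. SAP 8.3.1 states: "TEAE are defined as adverse events with onset date on or after the first treatment". For the companion incidence endpoint, SAP 8.2.3.3 states: "The proportion of subjects with at least one hospitalization during the treatment phase will be presented for the two treatment groups". The readable part of 8.2.3.3 gives no start date of its own.

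**The concern.** The endpoint is meant to cover the treatment phase, and that phase begins with the first infusion on Day 0. An admission later that day has a date equal to the first-dose date, not after it, so the rule in 7.8.3 passes over it. The same admission would be a treatment-emergent event under SAP 8.3.1 and, because it is a hospitalization, a serious adverse event under Protocol 9.3.

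The case is foreseeable. Protocol 3.1 requires sites to be equipped for acute allergic reaction, and Protocol 7.7 keeps subjects under observation for 30 minutes after every infusion. At stake is whether the hospital-day summary covers the period its title names. With 40 subjects per arm, that summary may rest on very few stays.

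**Working it through.** The plan gives no figure to reproduce here, so the check applies the written rule to example stays.

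**Inputs**
- Start bound (SAP 7.8.3): admission date > first-dose date.
- End bound (SAP 7.8.3): admission date < last-dose date.
- Formula (SAP 7.8.3): duration = discharge − admission + 1.
- First-dose date: Day 0 (Protocol 4.2.1). Protocol 7.4 calls the day of first dose Day 1. This does not matter here, because the rule refers to the dose date and not to a day number.
- Stay lengths: assumed for illustration.

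**Step 1. Subject dosed again after discharge, so the end bound is met.** The second column shows an inclusive start (admission date ≥ first-dose date). The last column shows the softer reading, in which the part of the stay after Day 0 still counts.

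| Stay | Inclusive start | As written, plain reading | As written, softer reading |
|---|---|---|---|
| Day 0 to Day 0 | 0 − 0 + 1 = 1 | none | 0 |
| Day 0 to Day 1 | 1 − 0 + 1 = 2 | none | 1 |
| Day 0 to Day 2 | 2 − 0 + 1 = 3 | none | 2 |
| Day 0 to Day 7 | 7 − 0 + 1 = 8 | none | 7 |
| Day 1 to Day 3 | 3 − 1 + 1 = 3 | 3 | 3 |

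The plain reading loses the whole of a Day 0 stay. The softer reading loses one day, which is everything for a same-day discharge. Admissions from Day 1 onward are unaffected by the start bound.

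**Step 2. Subject not dosed again.** First dose and last dose are both Day 0. As written, a Day 0 admission must satisfy 0 > 0 and 0 < 0, and fails both. With only the start bound changed it must satisfy 0 ≥ 0 and 0 < 0. The first condition now holds, but the second still fails, so the stay remains excluded.

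**Step 3. Comparison with the other boundaries.** The treatment-emergent rule (SAP 8.3.1) includes the day of first treatment. Adverse event reporting (Protocol 9.2) begins at the first treatment visit. Both put a Day 0 admission that follows the infusion on the treatment side of the line. The readable start rule in 7.8.3 does not.

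**The case against.** Several objections have force.

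- **The word occurring.** SAP 7.8.3 does not say admitted. A Day 0 to Day 2 stay also occurs on Days 1 and 2, so full exclusion is not certain. This stands. However, the SAP has no rule for splitting a stay at the start of the window, its formula runs from the admission date, and even this reading drops the Day 0 day.
- **The first-infusion case may fall to the other bound.** Protocol 5.2 lists a serious adverse event judged related to study medication among the reasons for stopping treatment. If the subject stops, the end bound removes the stay whatever the start bound says. This stands and limits what a start-bound edit can achieve.
- **Bias.** A reader might infer that the rule favours Ampligen, because drug-caused stays arise in one arm only. The documents do not support this. The rule is the same in both arms, admissions after saline or from unrelated causes are dropped as well, and no first-infusion admission rate is given.
- **Share affected.** With 24 infusions (12 weeks × 2), a reader might assume that the first carries r times the risk of each other one. The share of infusion-day admissions falling on Day 0 is then r/(r + 23): 4.2% at r = 1 and 5/28 = 17.9% at r = 5. Nothing in the documents supports a value of r above 1, and the result is not a share of all stays.
- **Conflict with incidence.** A reader might conclude that a subject will be counted as hospitalized with no hospital days. SAP 8.2.3.3 breaks off in the released text, and the missing part could set the same window. The mismatch is something to check, not an established fault.
- **Importance.** The study is unpowered, the endpoint is exploratory, and the event would still appear in the adverse event summaries and subject listings. This stands.

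**Conclusion.** The point holds as a minor defect of wording. On its plain reading, SAP 7.8.3 calculates no duration for an admission on Day 0 that follows the first infusion: 0 against 3 days for a Day 0 to Day 2 stay. On the softer reading the loss is one day. Either result is out of line with an endpoint defined over the treatment phase and with the SAP's own treatment-emergent rule.

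The direction of any bias and the proportion of stays affected cannot be determined from the documents. For scale only, an assumed Day 0 admission risk of 0.5% to 2% gives 40 × 0.005 = 0.2 to 40 × 0.02 = 0.8 subjects in an arm of 40, so the practical effect is probably no subject or one. No primary, secondary or safety conclusion depends on it.

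**What to change.** 1. In SAP 7.8.3, replace "hospitalization(s) occurring after the date of first study treatment administration" with wording that admits any stay whose admission date is on or after the first-dose date, except an admission documented as preceding the first infusion. Keep the rule on dates: Protocol 9.2 lists onset and end dates for adverse events, and the readable text does not show that an admission time is collected.
2. Revise the end bound in the same sentence so that a subject whose first dose is also the last is not excluded automatically. State which end date the formula uses for a stay that begins on the last-dose date and runs past it.
3. Confirm that the incidence endpoint in SAP 8.2.3.3 uses the same start.
4. While editing, correct the reference in SAP 8.2.3.4, which sends the reader to Section 7.8.4 for a formula that stands in 7.8.3.

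The cost is a few phrases in the SAP, settled before unblinding, with no new visits or assessments. The one added task is to check that any Day 0 admission did not precede the infusion. Where the records do not settle the order, the stay counts by default.

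### SAP 7.8.3 counts hospital stays and deaths over two different windows, and its wording drops an admission on the day of the first infusion

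*SAP*

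**What the plan says.** The endpoint is "Duration (days) of hospitalization during the treatment phase" (SAP 2.6.3), listed as exploratory. SAP 7.8.3 gives three rules for it.

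- **Stays.** Duration is discharge date minus admission date plus 1, calculated only for hospitalizations "occurring after the date of first study treatment administration and prior to the date of last study treatment administration". If the subject is still in hospital at the last treatment, "the date of last treatment will be used for the calculation". Multiple stays are summed.
- **Deaths.** "All deaths within 91 days will be considered censored on Day 91". The reason given is that "Conceptually, a death corresponds to an infinite length of hospitalization". The SAP adds that censoring at Day 91 or at any later day leads to the same answer, because "both correspond to giving deaths the worst rank".
- **Start of the window.** Stays are "hospitalization(s) occurring after the date of first study treatment administration". For adverse events, SAP 8.3.1 starts earlier: "TEAE are defined as adverse events with onset date on or after the first treatment".

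The companion endpoint in SAP 8.2.3.3 is the proportion of subjects with at least one hospitalization in the treatment phase. The visible text of SAP 8.2.3.4 says only where the duration formula is to be found and shows no analysis method.

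**The concern.** The variable is a sum of observed hospital days in outpatients, most of whom will probably have none. The death rule follows the logic of time to discharge in inpatients, where a patient who dies is never discharged and censoring has a meaning. Applied to a sum of days, it causes four problems.

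1. Stays and deaths are counted over different periods, and the difference depends on how early the subject stopped infusions.
2. Nothing in the death rule requires an admission. A subject who died without one would have no hospitalization under SAP 8.2.3.3 and the longest hospitalization here.
3. The claim that any later day gives the same answer is true of ranks. It is not true of a mean, a total or a standard deviation.
4. Apart from deaths, an admission on the day of the first infusion is not counted. The protocol plans for acute events on infusion days, with emergency equipment at the site (Protocol 3.1) and 30 minutes of observation after every infusion (Protocol 7.7).

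At stake is whether the reported figure is what its label says, and whether two programmers working from SAP 7.8.3 would derive the same value.

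**Working it through.** **Inputs.** First infusion at V2 = Day 0 (Protocol 4.2.1). Infusions twice weekly for 12 weeks, so 24 infusions from V2 to V25. V27 is 2 weeks after V25 (SAP 2.1.2.1), ± 3 days (SAP Appendix 1). 40 subjects per arm (SAP 2.3). The two weekly infusions are taken as 3 or 4 days apart, as in the documents' example schedules.

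**Where the stay window closes for a full course.** The last infusion is the second one of week 12: 11 × 7 + 3 = Day 80, or 11 × 7 + 4 = Day 81.

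**Where the death window closes.** Day 91 = 13 × 7. The gap is 91 − 80 = 11 days or 91 − 81 = 10 days. Protocol 7.4 calls the first-dose day Day 1; on that count the last dose is Day 81 or 82 and the gap is 10 or 9 days. Day 91 is not the nominal end of study either: V27 falls on 80 + 14 = Day 94 or 81 + 14 = Day 95.

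**Subjects who stop early.** Taking the last treatment as each subject's own last infusion, with a 3-day spacing:

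| Infusions received | Last infusion | Days to Day 91 when a death counts but a new stay does not |
|---|---|---|
| 24 | Day 80 | 91 − 80 = 11 |
| 12 | 5 × 7 + 3 = Day 38 | 91 − 38 = 53 |
| 8 | 3 × 7 + 3 = Day 24 | 91 − 24 = 67 |
| 1 | Day 0 | 91 − 0 = 91 |

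An admission after which the subject receives no further infusion begins after the last dose, so it adds nothing to the endpoint. A death following that admission, up to Day 91, takes the worst rank.

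**Does Day 91 deliver the worst rank?** Yes, under the present rules. The longest single countable stay runs from Day 1 to the last infusion: (80 − 1) + 1 = 80 days, or (81 − 1) + 1 = 81 days. Both are below 91.

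**Effect of one death in a rank analysis.** Assume a two-sided Wilcoxon rank-sum test (normal approximation), 40 per arm, and non-admitted survivors scored 0. The p-value range is without and with continuity correction.

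| Admissions per arm (5 days each) | Deaths, one arm vs other | p |
|---|---|---|
| 0 | 1 vs 0 | 0.32 to 0.33 |
| 0 | 4 vs 0 | 0.041 to 0.043 |
| 2 | 1 vs 0 | 0.63 to 0.64 |
| 2 | 4 vs 0 | 0.12 |

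**Effect of one death on a mean, if one were reported.** Scored as 91, one death adds 91/40 = 2.275 days to its arm. Assume 2.5% to 10% of the arm is admitted for 3 to 14 days. The arm mean is then 0.025 × 3 = 0.075 to 0.10 × 14 = 1.40 days without the death. With one never-admitted death it is 0.075 + 2.275 = 2.35 to 1.40 + 2.275 = 3.675 days. The admission rates and lengths of stay are assumptions; the documents give none.

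**The case against.** A worst rank for death is a recognised composite strategy. Simply deleting it would let an early death score few or no hospital days and so look favourable. That stands, and it is why removal is not recommended here.

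Day 91 also has some basis. It is 13 weeks, the primary outcome is read at week 13, and SAP 2.6.3 describes MoCA at week 13 as within the treatment phase. The calendar above is nominal, since the day origin is inconsistent and the holiday scheduling guide is not shown. This makes Day 91 understandable. It does not make it the window that SAP 7.8.3 applies to stays, and the gap is large for early stoppers.

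The sentence limiting the calculation to hospitalizations in the window could be read as limiting the death rule to admitted subjects. Inclusion of never-admitted deaths is therefore the literal reading but not the only one, and the text has to choose.

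A reader might infer that one death would dominate the comparison of arms. The documents do not support that. No mean is planned in the visible text, and the only clue, the reference to ranks, points to a rank analysis, in which one death against none is far from significance.

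Finally, deaths and first-day events are not lost to the trial. SAP 8.3.1 tabulates adverse events leading to death and includes events on the first treatment day, and hospitalization is a criterion for a serious adverse event (Protocol 9.3). The omission affects this endpoint only.

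**Conclusion.** The point holds as an inconsistency between stated rules. For a full course, deaths count about 10 days beyond the point where stays stop; for a subject who stops halfway the excess is 53 days. The start of the window excludes a first-infusion-day admission that SAP 8.3.1 would treat as treatment-emergent. The language of censoring and of the same answer is sound only if the analysis uses ranks, and the visible text should say so.

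The impact is low. The endpoint is exploratory, SAP 5 states that there is no formal hypothesis testing, and the primary and secondary outcomes are untouched. Few deaths are expected in adults aged 18 to 60 with these exclusions, which is an assumption. The shift of 2.3 days per death applies only if a mean is reported with deaths scored 91 and non-admitted subjects scored 0, and the visible text states none of these. The first-day omission does not depend on any death.

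**What to change.** 1. In SAP 7.8.3, count stays that begin on or after the date of first study treatment.
2. State one window for stays and deaths, the same for every subject whether or not infusions stopped early, and truncate open stays at its end.
3. If deaths keep the worst rank, call the endpoint a composite of death and hospital days, analyse it by ranks only, and state that deaths without admission are included. Show observed hospital days and deaths on separate lines.
4. Assign deaths a rank worse than any stay and drop the term censored. The value 91 is not safe under every choice of window: if stays are counted from Day 0 to Day 91, the longest is (91 − 0) + 1 = 92 days, which exceeds it.

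The cost is slightly more SAP wording, a revised derivation and one extra summary line. A common window for early stoppers needs admission and discharge dates after the last infusion; Protocol 5.4 already asks sites to attempt follow-up of these subjects, but completeness should be checked. The change should be made before unblinding, because a rule chosen after a death is known by arm would be post hoc.

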8. STATISTICAL METHODS

All statistical analyses will be performed using SAS[®] for Windows, version 9.4 or later. All data collected during this study will be presented in subject data listings.

All the efficacy analyses presented here will be conducted using mITT and PP populations. All safety analyses will be conducted using the Safety population.

8.1 Summarizing Disposition and Baseline Data

8.1.1 Subject Disposition and Withdrawals

There will be a detailed accounting of all subjects who sign an informed consent to participate in this trial.

8.1.2 Protocol Deviations

Protocol deviations will be identified and classified as minor or major before un-blinding according to the following categories:

8.1.3 Demographics and Baseline Characteristics

Medical history will be coded using the most current available version of Medical Dictionary for Regulatory Activities (MedDRA) and will be summarized by system organ class (SOC) and preferred term (PT).

8.1.5 Prior and Concomitant Medications

Prior medication is defined as any medication with an end date prior to the first treatment date.

8.1.6 Extent of Exposure and Treatment Compliance

8.2 Analysis of Efficacy Data

The primary analysis will be conducted on the mITT population.

The statistical tests for the primary efficacy endpoint and secondary endpoints will be two-sided with α =0.05.

8.2.1 Primary Outcome Measure and Estimand

8.2.1.1 Primary Outcome Measure

The primary efficacy outcome measure for this study is the change from baseline to week 13 in PROMIS® Fatigue Score (T-Score).

The Fatigue - Short Form 7a includes 7 questions and each question has a 5-point severity scale (Never, Rarely, Sometimes, Often, Always). The total score (range from 7-35) will be calculated and converted to the PROMIS® Fatigue Score (T-Score) per PROMIS

Fatigue Scoring Manual as which is included here as APPENDIX 3, Section 11.1. The higher in PROMIS® Fatigue Score (T-Score) represents the worsening of fatigue.

8.2.1.2 Estimand

The estimand for the primary outcome measure is described by the following attributes:

Treatment: Ampligen® vs. Placebo

Study Population: Adult patients with the Post-COVID Condition of fatigue.

Primary Efficacy Variable: Change from baseline to week 13 in PROMIS® Fatigue Score (T-Score)

Primary Efficacy Analysis Population: The Modified Intent-to-Treat (mITT) population is defined as the set of subjects who have received at least one dose of study treatment (Ampligen® or placebo).

8.2.2 Secondary Outcome Measures

8.2.2.1 Change from baseline to week 6 in PROMIS® Fatigue Score (T-Score)

Note: Additional PROMIS® Fatigue Score analysis (change from baseline) at week 6 and 13 will be performed excluding response to item, "How often did you have enough energy to exercise strenuously?"

Similar analysis methods used

for the primary endpoint will be applied to analyze the data from this outcome measure.

8.2.2.2 Change from baseline to week 6 and 13 in distance traveled during a 6-minute walk test

The 6-minute walk test (6MWT) will be assessed throughout the study. The 6MWT is a sub-maximal exercise test used to assess aerobic capacity and endurance. The distance covered over a time of 6 minutes is used as the outcome by which to compare changes in performance capacity.

Similar analysis methods used for the

primary endpoint will be applied to analyze the data from this outcome measure.

8.2.2.3 Proportion of subjects with minimal clinically important difference (MCID), defined as at least 54 m, in the Six-Minute Walk Test (6MWT) at the end of 12-week treatment phase

8.2.2.4 Change from baseline to week 6 and 13 in PROMIS® Cognitive Function Score (T-Score)

The Cognitive Function - Abilities - Short Form 8a includes 8 questions and each question has a 5-point severity scale from not at all to very much (1=Not at all, 2=A little bit, 3=Somewhat, 4=Quite a bit, and 5=Very much) ranged from 8-40. PROMIS® Cognitive Function Score (T-Score) will be converted from the total Short Form 8a score per PROMIS Fatigue Scoring Manual which is included here as APPENDIX 3, Section 11.2. The higher in PROMIS® Cognitive Function Score (T-Score) represents the better cognitive function.

Similar

analysis methods used for the primary endpoint will be applied to analyze the data from this outcome measure.

8.2.2.5 Change from baseline to week 6 and 13 in PROMIS® Sleep Disturbance Score (T-Score)

The Sleep Disturbance - Short Form 4a includes 4 questions with three 5-point severity scales from not at all to very much (1 or 5=Not at all, 2 or 4=A little bit, 3=Somewhat, 4 or 2=Quite a bit, and 5 or 1=Very much) and very poor to very good (5=Very poor, 4=Poor, 3=Fair, 2=Good, and 1=Very good) ranged from 4-20. PROMIS® Sleep Disturbance Score (T-Score) will be converted from the total Short Form 4a score per PROMIS Fatigue Scoring Manual which is included here as APPENDIX 3, Section 11.3. The higher in

PROMIS® Sleep Disturbance Score (T-Score) represents the worsening of sleep disturbance.

Similar

analysis methods used for the primary endpoint will be applied to analyze the data from this outcome measure.

